7.2.6.1.7 Relationship to the Study Product and/or Clinical Study Procedure

The Investigator is to determine whether there is a reasonable causal relationship between the occurrence of the AE and exposure to the study product and/or clinical study procedure.

Medical judgment should be used to determine the relationship, considering all relevant factors including the pattern of reaction, temporal relationships, relevant medical history, and confounding factors such as co-medication or concurrent diseases.

The expression “reasonable causal relationship” is meant to convey in general that there are facts or arguments to suggest a causal relationship (ICH E2A, Section IIIA 1).

The relationship assessment for an AE is to be completed using the following definitions as a guideline:

Reasonable Possibility:

According to the reporting Investigator, there is a reasonable possibility (i.e., suggestive evidence or arguments) that there is a causal relationship irrespective of the dose administered between:

- The study product (active or placebo) and the AE.
- The clinical study protocol procedure (e.g., bruising or marks from blood draws, injection related trauma, etc.) and the AE.

A two-point scale (Yes or No response) shall be used for the causality assessment. The Investigator shall be asked to indicate a response to each of the following questions in the eCRF:

- “Do you consider that there is a reasonable possibility that the event may have been caused by the study product?”, and
- “Do you consider that there is a reasonable possibility that the event may have been caused by the study product injection procedure?”

If any of these questions is answered Yes, the AE is considered related.

No Reasonable Possibility:

No suggestive evidence or arguments can be identified regarding a causal relationship between the study product or the clinical study protocol procedure and the AE.

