7.2.6.2 Reporting Procedures

7.2.6.2.1 Procedures for Reporting Adverse Events

The collection of AEs is from the time that a subject signs the ICF to their final visit.

At each post-enrollment visit, the Investigator (or sub-Investigator) will question the subject about AEs using an open non-persuasive question to elicit reporting of AEs, for example “Have you noticed any change in your health since the last visit?” Directed questioning and examination will then be performed as appropriate.

Any AE occurring during the AE reporting period, whether it is related to the study product or not, will be recorded immediately in the source document, and described on the AE form of the eCRF along with the date of onset, severity, relationship to the study product, and outcome, without omitting any requested and known information. Additional information will be requested under certain circumstances.

Adverse Events (AEs) assessed as related to the treatment or study procedure will be monitored until they have resolved or reached a stable condition. Other AEs will be monitored until the last visit if they have not resolved or reached a stable condition.

The Investigator will obtain and maintain in the subject’s files all pertinent medical records, information and medical judgment from colleagues who assisted in the treatment and follow-up of the subject. If necessary, the Investigator will contact the subject’s personal physician or hospital staff to obtain further details.

For SAEs (see Section 7.2.6.2.2) and pregnancies (see Section 7.2.6.2.3), the Sponsor is to be informed immediately by e-mail. The event must be reported by e-mail to the Safety Mailbox within 24 hours of receipt of the information (contact details in Section 7.2.6.2.2).

7.2.6.2.2 *Procedure for Reporting a Serious Adverse Event*

For a SAE occurring during the period of the clinical study, regardless of whether it is related to the treatment or not, and of whether it is expected or not, the Investigator must do the following:

1. Take prompt and appropriate medical action, if necessary. The safety of the subject is the first priority.
2. Ensure that the event is classified as an SAE (Section 7.2.6.1.3).
3. Complete the AE form provided in the eCRF as fully as possible.

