### (i) Treatment Emergent Adverse Events (TEAEs)

Adverse events (AEs) are to be monitored throughout the course of the study. The study period for the purpose of AE collection is defined as the period from the signing of a study specific informed consent to study exit for a subject. AEs recorded on the electronic case report forms (eCRFs) will be coded using the Medical Dictionary for Regulatory Activities (MedDRA). AEs will be classified as treatment-emergent adverse events (TEAEs) if the AE had an onset time greater than or equal to the time of the dose of study treatment.

Adverse events endpoints include:

- Incidence,
- Causality (related/not related to investigational product),
- Intensity (mild/moderate/severe),
- Time to onset,
- Duration,
- Leading to study withdrawal,
- Seriousness.

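### Protocol 7.2.6.1.7 defines blood-draw bruising as a related AE, but the two eCRF causality questions cannot record it

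*Protocol*

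**What the plan says.** Four pieces of text bear on the point, and none of them is redacted.

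- **Definition (Protocol 7.2.6.1.7).** A reasonable possibility exists when the AE may be linked to the product or, as the second limb, to a procedure: "The clinical study protocol procedure (e.g., bruising or marks from blood draws, injection related trauma, etc.) and the AE". The opposite class applies only on this condition: "No suggestive evidence or arguments can be identified regarding a causal relationship between the study product or the clinical study protocol procedure".
- **Questions and rule (same section).** The eCRF has two Yes/No items. One asks about "a reasonable possibility that the event may have been caused by the study product", the other about "a reasonable possibility that the event may have been caused by the study product injection procedure". The answers become a class by this rule: "If any of these questions is answered Yes, the AE is considered related".
- **Follow-up (Protocol 7.2.6.2.1).** "Adverse Events (AEs) assessed as related to the treatment or study procedure will be monitored until they have resolved or reached a stable condition". An open AE of any other kind is followed only to the last visit.
- **Analysis (SAP 1.6 (i) and 2.5.2).** The listed endpoint is "Causality (related/not related to investigational product"). Treatment-related TEAEs are tabulated by treatment group, SOC and PT. Treatment-related AEs are the only ones summarised for time to onset and duration.

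**The concern.** The definition covers every protocol procedure and gives blood-draw bruising as its first example. The instrument that applies the definition covers the product and its injection only. A cause that the protocol names therefore has no item on the form, and the visible text does not tell sites which answer to give.

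Two things depend on the answer. The first is follow-up: section 7.2.6.2.1 relies on a study-procedure relationship that no eCRF item captures. The second is the related-TEAE reporting. In a trial of an injected product, a bruise at the arm and a bruise at the glabella should not share a causality class by accident. SAP 2.5.2 also sets a missing start date to the day of treatment, so an undated blood-draw bruise coded Yes would be reported as starting on the day of treatment, as an injection bruise would. With up to 15 centers, the same event may be coded differently from site to site.

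**Working it through.** The plan gives no figure to reproduce. The check follows one blood-draw bruise through the texts.

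**1. Can it be a TEAE?** Protocol 7.2.4 refers to blood samples taken after baseline, and 9.1.3.1 summarises hematology, chemistry and antibodies by visit. Blood is therefore drawn after dosing, although the visits are redacted. SAP 1.6 (i) makes any AE with onset at or after dosing a TEAE. A bruise from a post-dose draw qualifies. A bruise with onset before dosing does not.

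**2. What class does the definition give?** Related. The bruise is the definition's own example, and it cannot meet the not-related class, which requires no evidence for either product or procedure.

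**3. What does the form give?**

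| | No/No (questions taken literally) | Yes on the injection item |
|---|---|---|
| True answer to the question asked? | Yes | No, the injection was not the cause |
| Class under the any-Yes rule | Not related | Related |
| Agrees with the protocol definition? | No | Yes, as a label |
| Agrees with the SAP's product-based endpoint? | Yes | No |
| Flagged by the form for follow-up beyond the last visit? | No | Yes |
| In the treatment-related tables? | No | Yes |

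The last row assumes that SAP 2.5.2 uses the protocol's any-Yes class; the visible SAP text states no other rule. Neither column agrees with all the texts.

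**4. How large could the table effect be?** The documents give no rate, so this is an illustration on assumptions. Let v be the proportion of subjects with a blood-draw TEAE (assumed 1% to 5%), s the share of these answered Yes (assumed 25% to 100%), and c = v × s, equal in all arms and independent of truly related events. With true related rate p (assumed 15% active, 5% placebo), the observed rate is p + (1 − p)c, and the difference is (15 − 5)(1 − c) points. Subjects per arm of 80 with such an event answered Yes = 80c.

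| v, s | c | 80c | Active | Placebo | Difference (points) | Ratio |
|---|---|---|---|---|---|---|
| none | 0 | 0 | 15.0% | 5.0% | 10.0 | 3.0 |
| 1%, 50% | 0.005 | 0.4 | 15.4% | 5.5% | 9.95 | 2.82 |
| 5%, 50% | 0.025 | 2.0 | 17.1% | 7.4% | 9.75 | 2.32 |
| 5%, 100% | 0.05 | 4.0 | 19.3% | 9.8% | 9.5 | 1.97 |

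The lowest corner (1%, 25%) gives c = 0.0025 and 0.2 subjects per arm. If every such event is answered No/No, c = 0 and the related rates do not change.

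**The case against.** A reader might infer that a blood-draw event is misclassified whichever way it is answered. The documents do not support that. A Yes yields the label that the protocol definition requires, and No/No yields the label that the SAP's product-based endpoint requires. Each answer fits one text and conflicts with another.

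A reader might also infer that the active-to-placebo comparison of related events is materially distorted. That rests on assumed rates, and on investigators affirming that the injection caused a bruise from a blood draw, which no text tells them to do. The ratio falls noticeably in the illustration only because the assumed placebo rate is low. The difference moves by at most half a point. No ratio is planned in the visible text, SAP 2.5 plans no inferential safety analysis, and nothing visible suggests that blood draws differ by arm. Answered literally, the form already keeps these events out of the related tables.

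A third inference is that procedure-related AEs lose their follow-up. All AEs are still followed to the last visit if unresolved, and SAEs are followed to an agreed resolution whatever their cause. An investigator could also apply section 7.2.6.2.1 from a procedure assessment made outside the two items, although section 7.2.6.1.7 does not say where that would be recorded.

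Finally, the definitions are offered as a guideline, AEs are MedDRA-coded, and all eCRF data are listed, so the cause can often be recovered from term and location.

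These points limit the consequences. They do not remove the conflict: a definition and the questions meant to apply it disagree within one section, and the follow-up rule has no eCRF item to identify the procedure-related events it covers.

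**Conclusion.** The inconsistency is real and should be corrected, but its effect is likely to be small. It consists of site-dependent coding of one class of event, slight dilution of related-TEAE rates across all arms if some sites answer Yes, and a follow-up gap confined to non-serious blood-draw events still unresolved at the last visit. The number of affected events cannot be estimated, because the sampling visits are redacted and no blood-draw AE rate is given. The figures in the illustration are assumptions, not findings. The conclusion that dilution is similar in all arms assumes that blood sampling and site coding do not differ by treatment, and nothing visible contradicts this under the double-blind design.

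**What to change.** Reconcile the definition, the eCRF items and the follow-up rule.

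- **Preferred.** Add a third Yes/No item on whether another study procedure, such as a blood draw, may have caused the event. Use all three items to identify AEs under Protocol 7.2.6.2.1. State in Protocol 9.1.3.1 and SAP 2.5.2 that the treatment-related tables, including onset and duration, use the product and injection-procedure items only.
- **Alternative.** Narrow the definition in 7.2.6.1.7 to the product and its injection procedure, and align the study-procedure wording in 7.2.6.2.1 with it.
- **If the eCRF can no longer change.** Before database lock, review AE term and location blind to treatment and derive an analysis flag for events due to blood draws. Leave the investigator's answers unchanged and describe the flag in the SAP.

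The cost is one more question per AE and a few sentences of text, or a short listing review.

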7.2.6.2 Reporting Procedures

7.2.6.2.1 Procedures for Reporting Adverse Events

The collection of AEs is from the time that a subject signs the ICF to their final visit.

At each post-enrollment visit, the Investigator (or sub-Investigator) will question the subject about AEs using an open non-persuasive question to elicit reporting of AEs, for example “Have you noticed any change in your health since the last visit?” Directed questioning and examination will then be performed as appropriate.

Any AE occurring during the AE reporting period, whether it is related to the study product or not, will be recorded immediately in the source document, and described on the AE form of the eCRF along with the date of onset, severity, relationship to the study product, and outcome, without omitting any requested and known information. Additional information will be requested under certain circumstances.

Adverse Events (AEs) assessed as related to the treatment or study procedure will be monitored until they have resolved or reached a stable condition. Other AEs will be monitored until the last visit if they have not resolved or reached a stable condition.

The Investigator will obtain and maintain in the subject’s files all pertinent medical records, information and medical judgment from colleagues who assisted in the treatment and follow-up of the subject. If necessary, the Investigator will contact the subject’s personal physician or hospital staff to obtain further details.

For SAEs (see Section 7.2.6.2.2) and pregnancies (see Section 7.2.6.2.3), the Sponsor is to be informed immediately by e-mail. The event must be reported by e-mail to the Safety Mailbox within 24 hours of receipt of the information (contact details in Section 7.2.6.2.2).

7.2.6.2.2 *Procedure for Reporting a Serious Adverse Event*

For a SAE occurring during the period of the clinical study, regardless of whether it is related to the treatment or not, and of whether it is expected or not, the Investigator must do the following:

1. Take prompt and appropriate medical action, if necessary. The safety of the subject is the first priority.
2. Ensure that the event is classified as an SAE (Section 7.2.6.1.3).
3. Complete the AE form provided in the eCRF as fully as possible.

Print and complete the SAE form. E-mail the completed form, accompanied by any other relevant information or anonymized medical records (e.g., laboratory test results) within 24 hours of receipt of the information to Safety Mailbox listed below. The demographics, medical history, drugs/therapies form, medical and surgical procedures form, and AE pages of the eCRF must be completed and available for review in the EDC system at the time of the report.

4. Immediately send the completed SAE report form to the Safety Mailbox via e-mail and discuss further actions to be taken.

5. Monitor and record the progress of the event until it resolves or reaches a clinically stable outcome, with or without sequelae. For all additional follow-up evaluations, send by e-mail all additional follow-up information on the SAE to the Safety Mailbox within 24 hours of receipt of the updated information. SAEs will be monitored until the Investigator and Sponsor agree that the event is satisfactorily resolved.
6. Obtain and maintain in his/her files all pertinent medical records, information, and medical judgments from colleagues who assisted in the treatment and follow-up of the subject. If necessary, contact the subject's personal physician or hospital staff to obtain further details.
7. Inform the Sponsor of the final outcome of the event. Send a revised or updated SAE form and AE form, if appropriate to the Safety Mailbox.
8. Prompt notification of SAEs by the Investigator to the Sponsor is essential so that legal obligations and ethical responsibilities towards the safety of subjects are met. The Sponsor has a legal responsibility to notify both the local regulatory authority and other regulatory agencies about the safety of a product under clinical investigation. The Sponsor will comply with country specific regulatory requirements relating to safety reporting to regulatory authorities, Institutional Review Boards (IRBs), and Investigators. Investigator safety reports are prepared for Suspected Unexpected Serious Adverse Reactions (SUSARs) according to local regulatory requirements and the Sponsor policy and are forwarded to Investigators as necessary. An Investigator who receives an Investigator

safety report describing a SAE(s) or other specific safety information (e.g., summary or listing of SAEs) from the Sponsor will file it with the Investigator's Brochure (IB) and will notify the IRB, if appropriate according to local requirements.

9. Comply with the applicable regulatory requirement(s) related to the reporting of SAEs to the IRB.

7.2.6.2.3 *Procedures for Reporting Pregnancies*

Any pregnancy occurring during the clinical study, where the fetus could have been exposed to the study product, must be monitored until its outcome in order to ensure the complete collection of safety data.

Pregnancies occurring during the screening period are considered as screening failures; they are recorded as such in the eCRF and no pregnancy form is to be completed.

If a subject becomes pregnant after the screening period, the Investigator is to do the following:

1. The subject does not need to be withdrawn from the clinical study, i.e. she may continue to attend the planned study visits, but no invasive procedure should be conducted (e.g. no sample taken for lab test).
2. Complete the Pregnancy Surveillance form – Part I: History and Start of Pregnancy as fully as possible. Send by e-mail this pregnancy form along with the exit form (if applicable) within 24 hours of receipt of the information to the Safety Mailbox listed above (and in Section 11.9).
3. Monitor and record the progress of the pregnancy until its outcome. Contact the subject's regular physician (general practitioner or gynecologist) or hospital staff to obtain further details and ask regular follow-up information.
4. Inform the Sponsor of the progress by tri-monthly updates until the final outcome of the pregnancy by completing the Pregnancy Surveillance form – Part I. For all the additional evaluations, send by e-mail the additional follow-up information to the Safety Mailbox within 24 hours of receipt of the information. If the subject can no longer be reached (lost to follow-up), documentation of the non-response/contact with two phone calls and a letter (certified with return receipt) is required.
5. At the outcome of the pregnancy, complete the Pregnancy Surveillance form – Part II: Course and Outcome of Pregnancy, as fully as possible. Inform the Sponsor by sending this pregnancy form to the Safety Mailbox within 24 hours of receipt of the information.
6. If the pregnancy leads to an abortion (voluntary abortion, spontaneous abortion or therapeutic abortion), *in utero* death or congenital anomaly, follow the procedure for declaration of an SAE (see Section 7.2.6.2.2).

7.3 Other Assessments

7.3.2 Pregnancy Test

For all women of childbearing potential, a urine pregnancy test will be performed at screening, baseline (prior to treatment), and at the Month 9/early termination visit. A negative pregnancy test is required for study inclusion. The result will be documented.

7.4 Appropriateness of Measurements

The efficacy and safety measurements used in this study are considered standard measurements, and are generally recognized as reliable, accurate, and relevant.

8.1 Description of Clinical Study Visits

Please refer to the Schedule of Assessments table in the Synopsis (Table 2).

A written, signed ICF (inclusive of HIPAA and photo consent) must be obtained prior to performing any clinical study-related evaluations and/or procedures. The subject must be provided with a fully completed, dated and signed copy.

A large, dark, rectangular redaction box covers the majority of the page content, starting below the header and ending above the footer. The redaction is composed of several horizontal bars of varying lengths, creating a striped effect. The top and bottom edges of the redaction are slightly irregular, suggesting a hand-drawn or heavily processed redaction. The rest of the page is white and contains no text or other markings.

Effective

2018-08-10 13:08

Effective date:

Version: 1.0

Effective

Effective date: 2018-08-10 13:08

Version: 1.0

Effective

Version: 1.0

Effective date: 2018-08-10 13:08

 GALDERMA	Title 43USD1801 Clinical Study Protocol Dysport	Doc id [REDACTED]
--	---	----------------------

Effective

Effective date: 2018-08-10 13:08

Version: 1.0

 GALDERMA	Title 43USD1801 Clinical Study Protocol Dysport [REDACTED]	Doc id [REDACTED]
---	---	----------------------

Effective

2018-08-10 13:08

Effective date:

Version: 1.0

43USD1801 Clinical Study Protocol Dysport

Doc id

A series of 15 horizontal black bars of varying lengths, decreasing in size from left to right. The bars are arranged in a descending staircase pattern, with the first bar being the longest and the last bar being the shortest. The bars are set against a white background.

9 STATISTICAL METHODS PLANNED

— 1 —

A dark gray horizontal bar with a slight curve at the right end, representing a scroll or a bar.

 GALDERMA	Title 43USD1801 Clinical Study Protocol Dysport [REDACTED]	Doc id [REDACTED]
---	---	----------------------

9.1.2.3 *Safety Population*

The safety population includes all subjects who were administered the study product [REDACTED]

9.1.2.4 *Imputation of Missing Data*

The Observed Cases (OC) will be used for all safety analyses as well as the exploratory analyses. The primary and secondary efficacy ITT analysis will be performed using baseline observation carried forward (BOCF), and repeated using multiple imputation (MI) for missing values. If deemed necessary, any analyses may be repeated using OC, BOCF, or MI as appropriate. [REDACTED]

9.1.3 *Data Presentation and Graphics*

Subject disposition, completion and discontinuation by study visit, protocol deviations, demographics and baseline characteristics, medical history, medical and surgical procedures, prior and concomitant medications, will be summarized by treatment group.

All efficacy variables will be summarized by treatment at each visit. [REDACTED]

9.1.3.1 Safety Analysis

A summary of all AEs will be provided, which will include:

- number of subjects who did not have an AE
- number of subjects with at least one AE and number of events
- number of subjects with at least one TEAE and number of events
- number of subjects with at least one related TEAE and number of events
- number of subjects with at least one TEAE by causality
- number of subjects with at least one TEAE by maximum intensity
- number of subjects with at least one TEAE leading to discontinuation
- number of subjects with at least one serious TEAE.

All TEAEs, treatment emergent SAEs, TEAEs by maximum intensity, TEAEs by causality, TEAEs by maximum intensity and causality, and TEAEs leading to discontinuation will be summarized by SOC and PT including number of subjects with at least one event, percentages, and number of events. All related TEAEs will also be summarized by time to onset and duration.

Data for hematology, blood chemistry, antibodies, and vital signs will be summarized by descriptive statistics with the value at each visit as well as the change from baseline. Shift tables for out of normal ranges results will be presented for hematology, blood chemistry and antibodies. The numbers and percentages of subjects with abnormalities in physical examination and vital signs will also be summarized. The results of the urine pregnancy tests will be listed.

